Since curcumin has the ability to increase insulin sensitivity, improve β -pancreatic function and is considered a safe supplement by the FDA, it has been decided to include therapy based on oral consumption of curcumin in subjects with prediabetes who show resistance to insulin. This scheme will allow to attack metabolically the barriers previously presented, as well as overcome barriers due to the inability to adjust to lifestyle changes.

4. Hypothesis

Oral supplementation with curcumin will increase insulin sensitivity measured through homeostatic model HOMA-Beta and the Matsuda index.

5. Objectives

General: Determine the effects of oral supplementation with curcumin to improve insulin sensitivity through the homeostatic models HOMA β and Matsuda index.

Specifics

- a. Determine the effect curcumin supplementation on the levels of: glucose, insulin (pre- and post-prandial), glycosylated hemoglobin, blood pressure, insulin sensitivity, lipid level (e.g., cholesterol, triglycerides, high and low lipoproteins density) and anthropometric measures (weight, body mass index, waist-hip ratio).
- b. Determine the effect of oral curcumin supplementation on models of insulin resistance measured through HOMA-IR and insulinogenic index.
- c. Determine if the consumption of curcumin supplementation will decrease the levels of inflammation markers: PCR, IL1, IL-6, FNT α .
- d. Determine the safety of curcumin supplementation by measuring the existence of possible side effects.

Methodology

Type and design of the study

It is a randomized, double-blind, placebo-controlled clinical trial.

Population and sample size.

142 pre-diabetic patients will be included, with prior informed consent, according to the criteria of the ADA [6]. The subjects will be randomly assigned to the treatment group with curcumin (n = 71) or the placebo group (control group, n = 71) using a fixed randomization scheme with assignment based on random numbers generated by a computer.

The calculus of the sample was performed with the statistical program Gpower 3.1, which resulted in 71 individuals per group, to obtain a statistical power of 80% in difference of means between two independent samples with an effect size of 0.5 in a two-tailed test, contemplating a 10% of losses during the study period.

Criteria of inclusion, exclusion and elimination.

Inclusion Criteria

- Men and women with age between 18 and 60 years old.
- With prediabetes:
 - a) Fasting serum glucose: 100-125 mg/dL

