To achieve the goals of the study and the correct analysis of the data, the variables will be divided into two groups, with the primary ones being expected to be modified by the treatment in the first term, which will define the success or failure of the study. It is expected that the secondary variables may or may not be affected by the treatment. In addition, possible confounders that interfere with the response will be included in the analysis.

- *Primary variables:* post-prandial glucose (2 horas), HOMA-IR, HOMA-β, Matsuda index and insulinogenic.
- *Secondary Variables:* anthropometric measurements, serum lipids, each determination of blood chemistry.
- *Potential confounders:* age and gender.

To determine the statistical difference in the categorical variables between the group of curcumin and placebo, X² will be used. The continuous variables at the beginning and at the end between the two groups will be compared using t student test of independent samples and an analysis of covariance (ANCOVA), which will be adjusted by the initial values of the primary and secondary variables of interest. In addition, the percentage differences between the groups in the values of the primary variables will be analyzed, using values of adjusted covariates (including age, gender, BMI) such as 100 x (curcumin group-placebo group) / placebo group of each study variable.

Table 2. Activities to be carried out during the study period.

Activity	1 st Semester	2 nd Semester	3 rd Semester	Last bimester
Selection and recruitment of patients	→			
Intervention	→			
Anthropometric, clinical and biochemical determinations (markers of stress and inflammation)	→			
Opening of randomization keys			↓	→
Analysis and captured of results			→	
Results publication				→

Ethical and biosecurity aspects

During the development of the project, all determinations and processes will be carried out under the norms and statutes pre-established, dictated by the Ethics and Biosafety Committee of this Hospital. The potential risks of the intervention will be made known to the volunteers before the intervention, which include:

- a) From the sample taking. In each measurement period (initial, intermediate and final) blood sampling is required, which comprises approximately 60 ml, with the risks inherent to blood collection such as bruising and the elimination of contagion risk due to the use of disposable plastic material, new in each subject and in each shot.

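### Five primary variables decide success, with no combining rule, multiplicity control, stated alpha or deciding test; if any one suffices at an assumed 0.05, the false-positive risk is about 10–23%

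*Combined protocol and SAP*

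**What the plan says.** The Statistical analysis section divides the variables into primary and secondary. The primary ones are those "which will define the success or failure of the study", and they are listed as "post-prandial glucose (2 horas), HOMA-IR, HOMA-β, Matsuda index and insulinogenic". No any/all rule, testing order, adjustment or significance level follows.

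Continuous variables at the start and end of the study "will be compared using t student test of independent samples and an analysis of covariance (ANCOVA"), the latter adjusted for initial values. Adjusted percentage differences are added for the primary variables. None of these analyses is designated as the one that decides.

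Other sections rank the variables differently. The Hypothesis concerns insulin sensitivity "measured through homeostatic model HOMA-Beta and the Matsuda index", and the general objective names the same two measures. Specific objective (b) covers "models of insulin resistance measured through HOMA-IR and insulinogenic index", and glucose is under specific objective (a).

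Population and sample size gives 71 per group "to obtain a statistical power of 80% in difference of means between two independent samples with an effect size of 0.5", two-tailed, with 10% losses. It gives no alpha and does not name the variable to which the effect size applies.

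**The concern.** A plan that says certain variables determine success must also say how. Here a reader could declare success from one significant variable out of five, or require all five, and the text supports both. It could also be read as allowing either of two tests per variable.

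Nothing in the document fixes the choice before the randomization keys are opened, a step scheduled in Table 2. The choice could therefore be made with the results in view. Under the permissive reading, the chance of a false claim exceeds the single-test level that the sample size implies. Under the strict reading, the 80% power calculated for one comparison is not the power of the trial.

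**Working it through.** **Inputs from the document.** Power 80%, standardised difference 0.5, two-tailed, 10% losses, 71 per group (Population and sample size); five primary variables (Statistical analysis).

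**Assumptions, not in the document.** Two-sided alpha 0.05; 64 evaluable per arm; equal correlation ρ between variables, from 0 to 0.9; baseline–final correlation r of 0.5 to 0.7; for power, d = 0.5 (in final-value SD units) on every variable.

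**1. Reproducing the sample size.** A two-sample t-test (noncentral t) with d = 0.5, power 0.80 and two-sided alpha 0.05 needs 63.8, so 64 per group. Allowing for losses, 64/0.9 = 71.1, or 64 × 1.1 = 70.4, which rounds up to 71. Strict rounding up of the first would give 72. Before losses, alpha 0.01 needs 96, alpha 0.025 needs 78 and one-sided 0.05 needs 51. None of these leads to 71, so two-sided 0.05 for a single comparison is the level the calculation implies.

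**2. Any one variable suffices.** With independent variables and one test each, the risk is 1 − 0.95^5 = 1 − 0.774 = 22.6%. For two variables it is 1 − 0.95^2 = 9.75%. Correlated one-test cases use the multivariate normal with a cut-off of |z| > 1.96. The either-test rows come from simulated trials with 64 per arm (20,000 per scenario).

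| False-positive risk (%) | ρ = 0 | 0.3 | 0.5 | 0.7 | 0.9 |
|---|---|---|---|---|---|
| Five variables, one test each | 22.6 | 20.9 | 18.3 | 14.8 | 10.2 |
| Two variables (hypothesis), one test each | 9.8 | 9.5 | 9.1 | 8.4 | 7.0 |
| Five, t-test or ANCOVA counts, r = 0.5 | 31.1 | 28.8 | 25.6 | 21.3 | 14.4 |
| Five, t-test or ANCOVA counts, r = 0.7 | 35.4 | 32.4 | 28.7 | 23.5 | 16.5 |

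Even a single variable tested both ways carries 7.0–8.4%.

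**3. All five required.** Each test is at 0.05 and all must pass, so the error cannot exceed 5%. Under the global null the simulated error was at most 1.7%. With independent t-tests, power is 0.801^5 = 33%. Simulated power:

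| Power to pass all five (%) | ρ = 0 | 0.3 | 0.5 | 0.7 |
|---|---|---|---|---|
| t-test | 33 | 44 | 52 | 59 |
| ANCOVA, r = 0.5 | 58 | 66 | 70 | 75 |
| ANCOVA, r = 0.7 | 88 | 89 | 91 | 92 |

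**4. Power per variable at 64 per arm.** ANCOVA raises the effective difference to 0.5/√(1 − r²), which is 0.577 at r = 0.5 and 0.700 at r = 0.7.

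| Power (%) | alpha 0.05 | 0.025 | 0.01 |
|---|---|---|---|
| t-test | 80.1 | 71.2 | 58.5 |
| ANCOVA, r = 0.5 | 90.0 | 83.9 | 74.1 |
| ANCOVA, r = 0.7 | 97.6 | 95.3 | 90.9 |

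The columns correspond to one primary variable, Holm's first step for two variables, and Holm's first step for five.

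**The case against.** The omission itself is not in dispute. The strongest objections concern the figures and the supporting points.

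- **The correlations are a grid and do not describe this trial.** By the plan's own formulas, HOMA-IR, HOMA-β and Matsuda share fasting glucose and insulin, while 2-hour glucose enters neither HOMA index. Neither ρ = 0 nor a uniform 0.9 is realistic. This is fair. Illustrative simulations that build the indices from shared glucose and insulin values, with assumed variances, gave about 17–19% with one test per variable and 25–27% if either test counts. These lie inside the ranges above.
- **The all-five power figures are not bounds.** HOMA-β rises with fasting insulin while Matsuda falls, so in the direction of benefit the two can be negatively correlated, which the grid excludes. This also stands, and the figures should be read as illustrations. One simulation from the plan's formulas put all-five t-test power at about 40%.
- **General and specific objectives are not primary and secondary tiers.** True, so the placement of HOMA-IR under a specific objective proves little by itself. The mismatch between a two-measure hypothesis and a five-variable success criterion remains.
- **The t-test may be meant for baseline only, with ANCOVA at the end.** That reading is natural, because a baseline-adjusted ANCOVA cannot be the baseline comparison. It removes the either-test inflation and leaves the five-variable problem untouched.
- **All five may be intended.** The plan does not say so. If it were intended, the cost would move from false positives to power.

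**Conclusion.** The concern holds and should be fixed before unblinding. The trial's criterion for success is undefined: five variables decide it, with no combining rule, alpha, multiplicity control or designated test, and with a sample size built for one unnamed comparison.

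If any one variable counts at an assumed two-sided 0.05 with one test each, the false-positive risk is about 10–23%, depending on correlation, or two to more than four times the nominal level. If either test counts, it is about 14–35%. If all five are required, error is controlled, but whether power reaches 80% depends on the test used and on correlations that the document does not give.

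Confidence in the omission is high. The ranges depend on the assumed alpha and correlations.

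**What to change.** Before the randomization keys are opened:

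1. State two-sided alpha 0.05.
2. Name the baseline-adjusted ANCOVA of the week-12 value as the only deciding test. The end-of-study t-test and the percentage differences become descriptive, and no inference is drawn from baseline t-tests.
3. Choose one of two structures. **(a)** Name one primary variable from the hypothesis, for example Matsuda, and test the other four as secondary in a fixed order or with Holm. **(b)** Keep the hypothesis's two variables, or all five, as primary with Holm.
4. Say which variable the effect size of 0.5 refers to.

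The same edit could usefully list the ANCOVA covariates and say which direction of HOMA-β counts as benefit.

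**Cost.** Option (a) changes wording only. With 64 evaluable per arm, power for the primary variable is 80% by t-test and about 90–98% by ANCOVA at r = 0.5–0.7. Option (b) is also a wording change but lowers power at Holm's first step. For two variables it is 71% by t-test or about 84–95% by ANCOVA; for five it is 58.5% by t-test or about 74–91% by ANCOVA. Restoring 80% by t-test at alpha 0.01 would need 96 per group, or 96/0.9 ≈ 107 after losses. Under either option, the sponsor can no longer claim success from whichever unadjusted variable happens to be significant.

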- Anthropometric measurements: weight, height, waist circumference, hip circumference, waist-hip circumference ratio and body fat percentage. They will be measured using an electric bio impedance scale and a measuring tape.

- Clinical: It will be determined in the Central Laboratory by standard methods and/or automated equipment, and includes the following:
 - a) Systolic blood pressure and diastolic blood pressure.
 - b) Blood chemistry: insulin, triglycerides, cholesterol, HDL cholesterol, LDL cholesterol, uric acid, creatine, urea, BUN, alanine amino transferase, alkaline phosphatase, glutamyl transferase, lactic dehydrogenase, glycosylated hemoglobin, direct bilirubin, indirect bilirubin, total bilirubin.
 - c) Blood count
 - d) Inflammation markers: PCR, IL 1, IL6, TNF- α .
 - e) Glucose tolerance curve: Fasting serum glucose and at 30, 60, 90 y 120 min after the oral dose of glucose (75 gr).
 - f) Parameters of insulin resistance and sensitivity under the following formulas
 - g) HOMA-IR: $(\text{Insulin } \mu\text{U/ml})(\text{Glucose mg/dl})/405$.
 - h) Matsuda index: $10,000/\sqrt{[(\text{basal glucose})(\text{basal insulin})*(\text{glucose})(\text{insulin})]}$
 - i) Insulinogenic: $\Delta \text{ insulin}/\Delta \text{ glucose}$.
 - j) HOMA1-%B: $(20)(\text{FPI})/(\text{FPG} - 3.5)$

Procedure

Intervention

Participants who meet the inclusion requirements and wish to participate in the study will sign an informed consent. 142 individuals will be included, who will be randomized to receive curcumin (n=71) or placebo (n=71).

- All participants will receive the same diet and exercise indications for a period of three months after enrollment (before randomization).

- Regarding the diet, all patients who enter the research protocol will be assessed and supervised. The feeding plan will be prepared by a nutritionist, individually for each patient, based on the recommendations of the American Diabetes Association 2018, with the following: Carbohydrates 55%, proteins 20% and lipids 25%.

According to the needs of the patient, the quantity of kilocalories/day is calculated. For weight reduction 20 kcal/kg/day, weight maintenance 25 kcal/kg/day. Follow-up appointments will be made by nutrition: at the beginning, 4, 8 and 12 weeks after the start of the intervention.

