Individuals with the intervention will be administered 1g of curcumin in capsules per day deferred in two doses of 500 mg each. Each capsule should be taken orally at breakfast and lunch for 3 months. The dose of curcumin was extracted from previous studies with similar patients. Individuals in the placebo group will be given two capsules of starch (250 mg) daily at breakfast and lunch for 3 months. Due to curcumin having a characteristic yellow color, the placebo capsules will be the same color as curcumin capsules.

Data collection and measurements

During the intervention period: 3 measurements will be made by the research team: initial (week 0), intermediate (week 6) and final (week 12), as expressed in Table 1.

Table 1. Variables to be evaluated according to the measurement time during the intervention.

Variable	Initial	Intermediate	Final
Anthropometric measures	Yes	Yes	Yes
Biochemists and clinics	Yes	Yes	Yes
Glucose tolerance curve	Yes	No	Yes
Inflammation markers	Yes	No	Yes

Each participant will be given a format to record the consumption of capsules per day, which will deliver at each visit (intermediate and final) and the bottles must be returned to verify the information. They will be exhorted on the importance of acting truthfully and not alter the contents of the jars.

Double blind scheme

Both the randomization and the control of capsule consumption will be controlled by an investigator unrelated to data collection and sample processing. This researcher will be responsible for assigning each individual their corresponding treatment and giving them the capsules, which will be contained in a bottle of the same color, size and shape, for the curcumin and placebo capsules. Therefore, the researchers responsible for the project will not know during the intervention which individual receives placebo or curcumin.

Activities schedule

Since the entire study comprises 20 months, the activities will be carried out as shown in Table 2 after the project has been approved by the respective committees.

Statistical analysis

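### Week-6 anthropometry and biochemistry have no planned analysis, so participants lost or eliminated after week 6 add nothing to the week-12 comparison of these variables

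*Combined protocol and SAP*

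**What the plan says.** **Visits.** Data collection and measurements sets three time points: "initial (week 0), intermediate (week 6) and final (week 12), as expressed in Table 1". Two rows of Table 1 matter most here. They read "Biochemists and clinics Yes Yes Yes" and "Glucose tolerance curve Yes No Yes" for the initial, intermediate and final visits. Anthropometry is also taken at all three visits. Inflammation markers are taken only at the first and last.

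**Content of the biochemistry.** The list of continuous variables begins item b) with "Blood chemistry: insulin, triglycerides, cholesterol, HDL cholesterol, LDL cholesterol, uric acid, creatine, urea, BUN" and goes on to liver tests, HbA1c and bilirubin. Glucose is not in item b). Fasting glucose appears in item e), under the tolerance curve, and the section on ordinal variables also says that it comes from that curve.

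**Analysis.** The Statistical analysis section states: "The continuous variables at the beginning and at the end between the two groups will be compared". The methods are an independent-samples t test and "an analysis of covariance (ANCOVA), which will be adjusted by the initial values of the primary and secondary variables of interest". No analysis of week 6, no repeated-measures model and no method for missing data is given.

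**Status of the variables.** The five primary variables are 2-hour glucose, HOMA-IR, HOMA-β, the Matsuda index and the insulinogenic index. Anthropometry, lipids and blood chemistry are secondary.

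**Who leaves.** The Elimination Criteria cover participants who abandon treatment, have any side effect, or are diagnosed with diabetes during the trial. The plan does not say whether their collected values stay in the analysis.

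**The concern.** A comparison of week-12 values can use only participants who have a week-12 value. Someone measured at week 6 and then lost has given half of the planned follow-up and a blood sample. For the variables measured at week 6, the stated analysis ignores both.

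The more important matter is what the analysis assumes about those who leave. A baseline-adjusted ANCOVA of completers is unbiased if, given arm and baseline covariates, loss is unrelated to the outcome. A repeated-measures model that includes week 6 also allows loss to depend on the week-6 value of the variable being modelled.

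That difference is real in this trial. Leaving is tied to side effects, to abandoning treatment and to a diabetes diagnosis. HbA1c is measured at week 6 and is one of the values on which such a diagnosis could rest.

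**Working it through.** **1. Which variables have a week-6 value**

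| Variables | Where listed | Week 6 in Table 1 |
|---|---|---|
| Weight, waist, hip, body fat | Anthropometric measurements | Yes |
| Insulin, lipids, HbA1c, other chemistry | Clinical, item b) | Yes |
| 2-hour glucose, Matsuda, insulinogenic index | Need the tolerance curve, item e) | No |
| Inflammation markers | Clinical, item d) | No |
| HOMA-IR, HOMA-β | Formulas under Clinical, items g) and j) | Unclear |

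Both HOMA formulas need fasting glucose and fasting insulin. Two readings are possible:
- The formulas stand under Clinical, and Table 1 has a row "Biochemists and clinics" marked for week 6, so HOMA could be meant to be available then.
- Fasting glucose is named only with the tolerance curve, so on the literal text there is no week-6 glucose to put into the formulas.

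The heading cannot settle this. Inflammation markers, the tolerance curve and the Matsuda index also stand under Clinical, and none of them is available at week 6.

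**2. The plan's sample size**

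Inputs from Population and sample size: effect size 0.5, two-tailed, 80% power, 10% losses, 71 per group. The documents state no alpha, so 0.05 is assumed. The two-sample t test needs 64 per arm (power 80.1%), and 64 × 1.10 = 70.4, rounded up to 71. The stated figure reproduces.

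**3. Precision gained from week 6**

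Let n_c be the number per arm with week 12, n_6 the number with week 6, and r the correlation of week 6 with week 12 given baseline. For a likelihood-based model,

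n_eff = 1 / [(1 − r²)/n_c + r²/n_6].

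The correlation must be the one given baseline, because both the planned ANCOVA and the repeated-measures model adjust for baseline. The documents give no correlation. Assume a raw correlation ρ of 0.5 to 0.8, equal between all pairs of visits. Then

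r = (ρ − ρ²)/(1 − ρ²) = ρ/(1 + ρ),

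which is 0.5/1.5 = 0.33 to 0.8/1.8 = 0.44. Assume also that every loss follows week 6, so n_6 = 71.

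*10% loss:* n_c = 71 × 0.9 = 63.9.
- r = 0.333: 0.8889/63.9 + 0.1111/71 = 0.01548, so n_eff = 64.6.
- r = 0.444: 0.8025/63.9 + 0.1975/71 = 0.01534, so n_eff = 65.2.

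*20% loss:* n_c = 71 × 0.8 = 56.8.
- r = 0.333: 0.8889/56.8 + 0.1111/71 = 0.01721, so n_eff = 58.1.
- r = 0.444: 0.8025/56.8 + 0.1975/71 = 0.01691, so n_eff = 59.1.

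Power of the two-sided t test at a standardised difference of 0.5:

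| Loss | Completers only | With week 6 |
|---|---|---|
| 10% | 80.1% | 80.5–80.9% |
| 20% | 75.2% | 76.2–76.9% |

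If only half of the losses follow week 6, the 10% row becomes 80.3–80.5%.

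**The case against.** **ANCOVA at week 12 is a standard, valid analysis.** This stands. It can be used for all five primary variables, and at the planned 10% loss it keeps 80.1% power. If baseline correlates at 0.5 with week 12, the adjusted standardised difference is 0.5/√(1 − 0.25) = 0.58 and power with 63.9 per arm is already about 90%. The gain in power is no reason to change the model.

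**A reader might infer that two of the five primary variables certainly lose week-6 data.** The documents do not support this. Insulin is scheduled at week 6, but fasting glucose is tied to a curve that is not done then. If no fasting glucose is drawn at week 6, no primary variable is affected.

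**A reader might also compute a larger gain.** Putting 0.5 to 0.8 straight into the formula gives 81.1–82.7% at 10% loss. That is right only if 0.5 to 0.8 is the correlation given baseline. If it is the raw correlation, part of the information has already been used by the baseline adjustment.

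**The model alone may recover nothing.** This stands too. If elimination removes participants from the analysis, a repeated-measures model of those who remain learns nothing from those who left. The analysis set has to be settled together with the model.

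**Conclusion.** The point holds for anthropometry, insulin, lipids, HbA1c and the other blood chemistry. They are measured at week 6, no analysis uses that visit, and a participant without week 12 drops out of the final comparison. Such participants still enter the comparison at baseline.

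For HOMA-IR and HOMA-β the text is ambiguous, and the sponsor must resolve it.

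The size is minor: about 0.4 to 0.8 percentage points of power at 10% loss and 1.0 to 1.7 at 20%. These figures rest on an assumed alpha of 0.05, an assumed correlation given baseline of 0.33 to 0.44, and all losses falling after week 6. Earlier losses make the gain smaller.

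The main benefit is the weaker assumption about loss, whose value cannot be computed from the documents. It has limits. Each model accounts only for the week-6 value of its own variable, and no such model corrects for loss that depends on the unseen week-12 value.

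**What to change.** Before the randomisation keys are opened:

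1. State whether fasting glucose is drawn at week 6, and make Table 1 and the variable list agree.
2. For every continuous variable with a week-6 value, fit a repeated-measures model on weeks 6 and 12. Include baseline, visit, treatment, treatment by visit, baseline by visit, age and gender, with unstructured covariance. Take the week-12 treatment contrast as the estimate. Include HOMA-IR and HOMA-β if fasting glucose is drawn at week 6.
3. Include all randomised participants with any post-baseline value, and keep the values already collected from those who meet the elimination criteria.
4. Keep baseline-adjusted ANCOVA for the tolerance-curve variables. Inflammation markers likewise have no week-6 value.

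If week-6 sampling already includes fasting glucose, no new data are needed for any of this; if it does not, the model simply covers fewer variables. The week-12 target is unchanged. The cost is slightly more analysis work and, if HOMA is included, two model types across the primary variables.

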Chuengsamarn Set al, studied the effects of curcuminoids in the reduction of atherogenic risk in patients with diabetes mellitus type 2 (n = 213), with doses of 1.5 gr per day of curcuminoids, finding side effects in less than 1% of the sample, with a mean of 6-month follow-up, finding that intervention with curcumin significantly reduces pulse wave velocity, increases serum adiponectin levels and decreases leptin levels. As well as decrease in levels of triglycerides, visceral fat and total body fat (15).

Although follow-ups in similar studies with prediabetes have been performed at 6 months, finding significant differences, there are studies with 1 to 3 months follow-ups in obese patients or in metabolic syndrome, where significant differences have been found in lipid levels, bodyweight and inflammation markers. This is why, it is interesting to value the response of curcumin supplementation in less than 6 months, betting on a positive effect on insulin sensitivity after 3 months of intervention.

It has been noticed that the side effect of curcumin have not been reported when consumption is less than 12 g per day. At higher doses there may be presence of nausea and diarrhea. Without finding side effects when curcuminoids were used at doses of 1 to 1.5

g / day (15, 26, 27), this means that the 500 mg dose/12hrs is safe for curcumin supplementation.

2. Problem Statement

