- b) Of the intervention. According to the FDA, there have been no reported adverse reactions to the consumption of curcumin less than 12 g per day. At higher doses there may be presence of nausea and diarrhea. This protocol includes the consumption of 1 g per day and no adverse reactions have been reported, however, an instrument sheet of adverse reactions will be granted and the participants will be instructed to stop treatment if they face any secondary reactions such as nausea, dizziness, vomiting and/or diarrhea.

Relevance and expectations

In the case that treatment is positive, safe alternatives for prediabetes can be established. In addition, derived from the results, an article will be published in a high impact magazine and presented at a congress.

Available resources

We count with the human resources required for the proper development of the project. Within the research group are [name] [name], Resident doctor in the third year of the Internal Medicine specialty at the General Hospital of Mexico and student of a master's degree in Medical Sciences at the UNAM, and [name] [name], Health Sciences Chief department at UAM-Lerma, who has extensive experience in the design of studies and with the necessary facilities for the processing of samples.

A professional in nutrition will be hired, who will be in charge of supervising the food plan during the intervention.

Regarding the material resources, curcumin and placebo capsules are available for patients and the necessary material for the processing of samples for the determination of markers of oxidative stress and inflammation.

Resources to request

The necessary for the glucose tolerance curve: trutol, catheters, syringes, gauze, three-way stopcocks, test tubes for blood collection, enzymatic assay for insulin determination and laboratory tests.

Bibliographic references

1. Diabetes FId. FID, Federación Internacional de Diabetes, 2017. Atlas de la diabetes 2017 [Available from: <http://www.idf.org/diabetesatlas>
3. 2. Classification and Diagnosis of Diabetes: Standards of Medical Care in Diabetes-2018. *Diabetes Care.* 2018;41(Suppl 1):S13-s27.

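### A positive result would support a 12-week add-on metabolic effect, not safe alternatives; the safety objective has no planned analysis, and participants with side effects are eliminated

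*Combined protocol and SAP*

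**What the plan says.** **Intended conclusion.** Relevance and expectations: "In the case that treatment is positive, safe alternatives for prediabetes can be established".

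**What counts as positive.** The Statistical analysis section says the primary variables decide success or failure. They are 2-hour glucose, HOMA-IR, HOMA-β, the Matsuda index and the insulinogenic index. None is a safety variable.

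**The comparison.** The Intervention section gives all participants the same diet and exercise indications. A nutritionist writes an individual plan, with nutrition visits at the start and at 4, 8 and 12 weeks of the intervention. The control is placebo. Users of drugs that alter blood glucose are excluded.

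**The role given to curcumin.** The Problem Statement calls it an adjuvant. The Justification says the scheme will "overcome barriers due to the inability to adjust to lifestyle changes".

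**Safety.** Objective d is: "Determine the safety of curcumin supplementation by measuring the existence of possible side effects". Ethical and biosecurity aspects provides an adverse-reaction sheet. The Elimination Criteria list subjects who show any side effect, naming nausea and diarrhoea.

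**Laboratory tests.** The definition of variables lists "alanine amino transferase, alkaline phosphatase, glutamyl transferase", lactic dehydrogenase, bilirubins, urea, BUN, an item printed as creatine, and a blood count. Table 1 schedules biochemistry at weeks 0, 6 and 12. The secondary variables are "anthropometric measurements, serum lipids, each determination of blood chemistry".

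**The concern.** The expected conclusion makes two claims that the success criterion does not address: that curcumin is safe, and that it is an alternative. If the plan is followed as written, a significant change in metabolic indices could be published as both.

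The safety gap goes beyond wording. A stated objective has no variable, denominator, table or interval in the analysis section, and an elimination rule names the very participants the objective is meant to count. If eliminated participants leave the data set, the report could show few or no side effects because of how the set was formed.

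**Working it through.** **1. The planned size, and what drives it.** Inputs from Population and sample size: effect size 0.5, two-tailed, 80% power, 10% losses. Alpha is not stated; 0.05 is assumed.

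- Two-sample t test: 63.8, so 64 per group (normal approximation: 63).
- Adding 10%: 64 × 1.10 = 70.4, so 71, which matches the plan. Dividing instead gives 64 / 0.90 = 71.1, so 72.

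The 71 per group is thus reproduced. It comes from a difference in means on a continuous outcome; no safety event rate enters it.

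**2. What 71 treated people can say about safety.** The Intervention section states: "142 individuals will be included, who will be randomized to receive curcumin (n=71) or placebo (n=71"). Treatment lasts 12 weeks, so exposure is at most 71 × 12/52 = 16.4 person-years, and no visit after week 12 is described.

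Exact upper bound with zero events in n, at n = 71:

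- One-sided 95%: 1 − 0.05^(1/71) = 4.1%
- Two-sided 95%: 1 − 0.025^(1/71) = 5.1%

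Chance of seeing no event at a true rate p, (1 − p)^71. The protocol gives no expected rate, so a range is shown:

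| Assumed true rate | Chance of no event in 71 |
|---|---|
| 0.5% | 70% |
| 1% | 49% |
| 2% | 24% |
| 5% | 3% |

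The 1% row is the nearest to a figure in the Background, which reports a cited study "finding side effects in less than 1% of the sample, with a mean of 6-month follow-up". That study was in type 2 diabetes at 1.5 g per day, so it is a reference point and not this trial's expected rate. The Background also cites the same reference for finding no side effects at 1 to 1.5 g per day; these two statements should be reconciled.

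**3. Objective d against the Elimination Criteria.** Suppose k of the 71 treated have a side effect. If all k are removed from the analysed set, what remains is 0 events in 71 − k people, whatever k is. The documents do not say whether eliminated participants stay in the safety count, so this is a possible consequence and not a certain one.

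**4. Objective d against the Statistical analysis section.** Side effects are in neither the primary nor the secondary list, and they are not among the coded nominal variables (gender, treatment, adherence, altered fasting glucose). Blood chemistry is compared between arms by t test and by ANCOVA adjusted for the initial value, which are comparisons of means. A few individuals with abnormal liver or renal values can leave a mean of 71 almost unchanged. The comparison described is at the beginning and the end, so the week 6 values have no stated use. The blood count is listed separately from blood chemistry and is not named in the analysis section.

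**5. What the comparison identifies.** Arm A is curcumin plus diet and exercise indications; arm B is placebo plus the same. Their difference is the effect of adding curcumin. Nothing in it compares curcumin with a drug, or with the absence of lifestyle advice. The Intervention section places the three months of diet and exercise before randomisation, while the nutrition visits run during the intervention. The timing is unclear, but it is the same for both arms.

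**The case against.** **The sentence is an aspiration.** It sets no endpoint or decision rule, and no estimate or test changes if it is reworded. This stands and limits the severity. It does not dispose of the missing analysis for objective d.

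**The word alternatives is open.** The text does not say alternative to what. The Background seeks low-cost, low-toxicity agents in contrast to drugs, and the Problem Statement speaks of an adjuvant. That is a fair reading, but there is no drug arm, so substitution for drugs is not tested either.

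**Safety may rest on earlier evidence.** The protocol relies on regulatory status and cited studies, and positive may refer to efficacy only. The wording allows this. Objective d, however, promises a safety answer from this trial.

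**The general rules may cover side effects.** Categorical variables are to be compared by χ². Side effects are never defined as a variable, so neither their coding nor their denominator is fixed.

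**The bounds are generic.** Any trial with 71 treated has them. That is true; they are a reason to report intervals, not to enlarge the trial.

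A reader might also infer more than the documents support:

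- That safety is read from symptoms alone. Liver and renal chemistry and a blood count are listed, and biochemistry is scheduled three times.
- That people who do not change their lifestyle are not studied. No criterion requires adherence to diet or exercise.
- That exercise is supervised. Only the diet is.
- That a zero-event bound among completers is useful. If those with side effects are eliminated, completers have none by construction.

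**Conclusion.** The concern holds within limits. The design can support a 12-week metabolic effect of curcumin added to a supervised diet and exercise advice, which agrees with the protocol's own description of an adjuvant. It cannot establish an alternative, because nothing it could replace is compared with it. It cannot establish safety: even with no events in 71 treated, rates up to 4.1% (one-sided 95%) or 5.1% (two-sided 95%) remain possible, and a 1% event would be missed 49% of the time. These figures assume that all 71 take curcumin and are counted, and that the chance of an event is the same and independent across participants.

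The more consequential part is internal: objective d has no analysis, and the elimination rule could remove the events it must count. Those sections must be reconciled. The severity is modest. The primary tests are unaffected, and the data needed are already to be collected.

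**What to change.** 1. **Conclusion.** In Relevance and expectations, and in the matching text of the Justification, state that a positive result would show a 12-week metabolic effect of curcumin added to a supervised diet and exercise advice. Describe short-term tolerability instead of claiming that safety is established.
2. **Side effects.** Under objective d, report the frequency by arm with exact 95% confidence intervals among all randomised participants who took at least one capsule, including those eliminated. State in the Elimination Criteria that elimination does not remove anyone from this count. This concerns the count only, not when treatment is stopped.
3. **Laboratory shifts.** Tabulate by arm the participants who move from within to outside the laboratory's reference limits after week 0, for the liver, renal and blood-count tests already listed. Show how many have no later sample. Clarify whether the item printed as creatine is the serum creatinine used in the exclusion criterion.

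The cost is one or two tables, some rewording and a less favourable stated conclusion. No new visits, samples or participants are needed.
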